To compare changes in anxiety symptoms between the two groups over time, we will use a longitudinal, mixed-model analysis containing terms for the intercept, treatment, time, and interaction between time and treatment. In separate analyses, we will compare changes in quality-of-life between the two groups over time using a similar mixed-model approach. The mixed-model analysis will allow us to nest patients by site. Any baseline characteristics found to be significantly different between bCBT and EUC will be included in the model, as will any differences in mental health service use. The four time points (baseline, 4-, 8-, and 12-month) will allow us to assess the immediate impact of treatment and the longer-term retention, improvement, or decay in outcomes. The treatment effect will measure differences between the intervention and control groups at baseline, and the time effect will measure whether there was an overall change over time in the outcome. The term of most interest will be the interaction between time and treatment, which will indicate whether there is a difference over time between the two groups. The use of the random-coefficient model will allow us to fit a line for each participant using his/her available data, including participants with missing values, and maximize the power to detect differences.

Secondary Analyses: Prediction of bCBT response and VVC-H use:

We will run two logistic regression analyses using only data from participants who received bCBT. In analysis 1, we will identify characteristics that predict response to treatment as defined as a reduction of 50% on the GAD-7. Predictor variables will include: baseline anxiety severity (GAD-7 score), presence of specific anxiety diagnoses (GAD, Panic, Social Anxiety, Other), medical comorbidities, and brief CBT-related factors (number sessions received and treatment engagement). In analysis 2, we will identify characteristics associated with VVC-H use. VVC-H

use will be classified as any (one or more VVC-H sessions) or none. Predictor variables will include: age, distance to VA facility in miles, medical comorbidities, depression and PTSD (presence or absence), and Veteran self-reported comfort receiving in-person VHA care and confidence using video-based services and technology.

Implementation Analyses (Exploratory):

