Step 3: Provider Inflation Factor. The bCBT sample size was then inflated to account for the intraclass correlation due to clustering of patients within providers⁴³. We also will adjust the sample sizes for both the bCBT and EUC groups to account for attrition. Because only participants receiving bCBT are assigned to a provider, we first determined the average number of bCBT patients per provider (87 bCBT patients/25 providers = 3.5 patients per provider). To account for clustering in the bCBT group, the number of bCBT patients is inflated by the factor $[1 + (\bar{m} - 1) c]$, where \bar{m} is the average number of bCBT patients per provider and c is the correlation among patients seen by the same provider. Based on the sample size of 87 bCBT patients and an assumed correlation among patients of .10⁴³, our inflation factor is 1.25 ($87 \times 1.25 = 109$). Finally, to account for attrition, we assumed an attrition rate at 1 year of 25% ($109 \times (1/0.75) = 145$) gives 145 bCBT patients. A similar clustering inflation factor was not used for the EUC group, as no providers are assigned. Attrition rate of 25% was assigned to the EUC group ($58 \times (1/0.75) = 78$), rounded to 80 for randomization. The final number of randomized patients equates to 225 (145 bCBT and 80 EUC).

Secondary Aims:

Prediction of bCBT response and VVC-H use (bCBT group only). To assess predictors of bCBT response and VVC-H use, at least 10 events per variable in the logistic-regression models are needed to have unbiased estimates of the sample variance of the regression coefficients⁴⁴. No sample-size calculations were conducted for secondary aim, but SAS[®] proc power (version 9.4)⁴⁵ indicated a sample of 145 is adequate for 80% power to test odds ratio of 2.5, and conservative estimates for sample size and assumptions necessary to run the analyses suggest the project will be appropriately powered for 10 variables⁴⁶. Secondary analyses will include 8 variables for aim 2A (bCBT response; model #1) and 8 variables for aim 2B (VVC-H prediction; model #2).

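### Under the protocol's own rule of 10 events per variable, the Aim 2 logistic models cannot carry the 10 predictors claimed or the 8 planned, if events are counted in the rarer outcome class

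*Protocol*

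**What the plan says.** Protocol section 5.6 (Sample Size and Power Calculations, Secondary Aims) sets a rule: "at least 10 events per variable in the logistic-regression models are needed". It notes that no sample-size calculation was done for this aim, reports that 145 patients give 80% power for an odds ratio of 2.5, and adds that conservative estimates "suggest the project will be appropriately powered for 10 variables". It then fixes the model size: "Secondary analyses will include 8 variables for aim 2A (bCBT response; model #1) and 8 variables for aim 2B".

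The 145 comes from Step 3 of the same section, where it is the number randomised to bCBT: "The final number of randomized patients equates to 225 (145 bCBT and 80 EUC". Step 3 reaches it by inflating 109 for dropout: "we assumed an attrition rate at 1 year of 25" per cent.

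Section 5.6 (Secondary Analyses) describes both models as "using only data from participants who received bCBT". Model 1 has GAD-7 response (a 50% reduction) as its outcome. Model 2 has any versus no VVC-H session. No expected response rate, VVC-H uptake or time point for response is given.

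**The concern.** The rule, the 10-variable claim and the 8-variable plan stand in one paragraph, and the sample does not appear large enough for the rule to allow either number. In a logistic model the information is limited by the smaller of the two outcome groups, and with 145 patients that group can never exceed half of them.

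Prediction of response and of VVC-H use is a stated secondary aim (section 3.0), and Step 2 of the sample-size section justifies the 60% allocation to bCBT partly by power for secondary outcomes. A reader is told that the models are adequately supported. If they are not, there is a risk of unstable coefficients and exaggerated odds ratios, and of chance predictors of response or video use being reported as findings.

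**Working it through.** **Inputs (Protocol section 5.6).** Rule: 10 events per variable. Claimed capacity: 10 variables. Planned: 8 per model. Randomised to bCBT: 145. Attrition: 25% at 1 year.

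**1. The plan's own 145.** 87 × 1.25 = 108.75, taken as 109; 109 / 0.75 = 145.3, taken as 145. The figure reproduces. It also shows that 145 is the number before attrition and 109 the number expected to remain at 1 year.

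**2. The claim of 10 variables.** Events are counted in the rarer outcome class, the standard reading. The largest possible count is floor(n / 2), and the maximum number of variables is that count divided by 10, rounded down.

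| n analysed | largest rarer class | events per variable with 8 | with 10 | maximum variables | outcome rate needed for that maximum |
|---|---|---|---|---|---|
| 145 | 72 | 9.0 | 7.2 | 7 | 48.3% to 51.7% (70/145 to 75/145) |
| 109 | 54 | 6.75 | 5.4 | 5 | 45.9% to 54.1% (50/109 to 59/109) |

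Eight variables need 80 events and ten need 100. Neither is reachable at any outcome rate, so the figure of 10 does not reproduce.

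**3. Less favourable rates (assumed, since none is stated).** At 40% or 60% the rarer class is 58 of 145 (58 / 8 = 7.25 per variable; at most 5 variables) or about 44 of 109 (43.6 / 8 = 5.45; at most 4). At 30% or 70% it is about 43 of 145 (at most 4) or about 33 of 109 (at most 3).

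**4. What the rule would require.** Eight variables need at least 2 × 80 = 160 analysed, or 160 / 0.75 = 214 randomised to bCBT at 25% attrition. Ten need 200 analysed, or 267 randomised. Both assume an even split.

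**5. Literal reading.** If only responders or VVC-H users count as events, 8 variables need a rate of at least 80/145 = 55%, and 10 need 100/145 = 69%. At 109 these become 73% and 92%.

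**6. Which n belongs to which model.**
- Model 1: section 5.6 lists baseline GAD-7, four diagnoses, medical comorbidities, number of sessions and engagement, 1 + 4 + 1 + 2 = 8. If response is judged at 12 months, n is about 109 and the limit is 5. An earlier time point would lose fewer patients, with a limit of 7 if none were lost.
- Model 2: section 5.5 takes delivery format from note templates and chart review, so follow-up attrition need not remove patients. The ceiling is 72 of 145, less any patients with no sessions, a group that section 5.3 expects to exist. Section 5.6 appears to list 7 predictors (age, distance, medical comorbidities, depression, PTSD, comfort with in-person care, confidence with video), against the 8 stated under Secondary Aims. Section 5.5 also names logistic access to video technology, which may be the eighth. Seven need 70 events, hence at least 140 analysed and a near-even split, so no more than 5 of the 145 could be lost from the analysis.

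**7. The odds ratio of 2.5.** Significance level, predictor type and event rate are not stated for this calculation. Assuming two-sided 0.05, a binary predictor gives at best about 0.78 power at n = 145 and 0.66 at n = 109 (evenly split predictor, 50% overall rate). A continuous predictor, with the odds ratio per standard deviation, needs (1.96 + 0.84)² / [p(1 − p)(ln 2.5)²], about 37 patients at p = 0.5 and 45 at p = 0.3. The 80% is therefore attainable under some assumptions, even at 109.

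**The case against.** The protocol says only events, not the rarer class, so a count of responders or VVC-H users could satisfy the rule. That is possible at the rates in step 5, but the protocol neither states nor assumes such rates. If more than half of patients have the outcome, the non-events become the limiting group.

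A reader might infer that both models support at most 5 predictors because only 109 patients remain. The documents do not support this. Model 2's outcome comes from records, and model 1 reaches 109 only if response is judged at 12 months. It could be judged at 4 months, or from the GAD-7 that providers record in sessions. Model 2 with the 7 listed predictors is not shown to fail, although it has almost no margin.

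A reader might also infer that the power statement for an odds ratio of 2.5 is false. That is not established: a continuous predictor can exceed 80%, and the best binary case at 145 falls only about 2 points short. The statement concerns a single odds ratio, however, and says nothing about how many coefficients a model can carry.

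Finally, the rule is a guide, the protocol ties it to the variance estimates of the coefficients, and 9.0 events per variable in the best case is a modest shortfall. It does not follow that the models will certainly be overfitted. What stands is that the protocol adopts the rule and then states a capacity that the rule does not allow.

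**Conclusion.** The 10-variable claim and the plan for 8 variables per model are inconsistent with the protocol's own criterion at any outcome rate, provided that events are counted in the rarer class. The best case is 9.0 events per variable for 8 predictors with all 145 patients. For response at 12 months it is 6.75 with 109. The supportable maximum is 7 variables with all 145 analysed, and 5 for model 1 if response is judged at 12 months, each only near an even split. On the literal reading the claim is unsupported rather than impossible, because no expected rate is given. The 109 assumes the planned attrition and a 12-month response. The point concerns a secondary aim and leaves the primary analysis and the randomised total of 225 untouched.

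**What to change.** In Protocol section 5.6:

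- Delete the statement about 10 variables.
- For each model, state the analysed n, the assumed event rate and the resulting maximum number of parameters: at most 5 for model 1 if response is judged at 12 months, and at most 7 for model 2. Define events as the rarer class, name the time point for response, and say whether patients with no sessions are included.
- Reconcile the predictor count for model 2 (7 listed, 8 stated).
- Either cut the predictors to the supportable number, for example by collapsing the four diagnosis indicators, or keep them with pre-specified penalised estimation (Firth or ridge). Label both models exploratory.
- For the odds ratio of 2.5, give the predictor type, event rate and analysed n on which the 80% rests.

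No extra patients or procedures are needed. The cost is fewer predictors or shrunken estimates. Collapsing the diagnoses gives up some of the disorder-specific question in Aim 2A, so penalised estimation may suit that aim better. The SAP text supplied covers only the primary aim, so the change belongs in the protocol and in any fuller SAP text on Aim 2.

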5.7 Withdrawal of Subjects

- Describe any anticipated circumstances under which subjects will be withdrawn from the research without their consent.
- Describe the consequences of a subject's decision to withdraw from the research and the procedures for orderly termination of participation by the subject (e.g., the subject contacting the investigator for an end-of-study visit).
- Describe procedures if a subject is withdrawn or withdraws from the intervention portion of the study but agrees to continue in the follow-up phases or for safety outcome purposes.

There is no foreseeable circumstance for which research participants will be withdrawn from the study without their consent. If a participant chooses to withdraw from the study, there will be no consequences. The subject will not lose any rights or permissions s/he currently receives. To

withdraw from the study, an individual will be asked to contact the study staff to inform of the decision and remove their participation status in the project databases.

bCBT patients who drop out of treatment will be allowed to continue with research follow-up assessments. The provider will be notified in one of two ways: 1) via the Veteran during the session; 2) the research staff will notify the provider that the Veteran no longer wishes to receive treatment. The Veteran's research file will be notated with withdrawal and that he/she is still willing to complete the follow-up assessments.

5.8 Subject Compensation

Veteran Participant Compensation:

Only Veteran participants will be compensated in the study. Study clinicians are not eligible for compensation given their VA appointment. Veteran participants will be compensated \$30 for each study assessment completed which will be at baseline, 4-month assessment, 8-month assessment, and 12-month assessment. There is a total of 4 study assessments which will allow a Veteran to be compensated up to a total of \$120.00 if all study assessments are completed. If a participant has electronic funds transfer set up with the VA or agrees to sign up, then they will be eligible to have the money deposited directly into their account. Veterans not interested in signing up for electronic funds transfer will receive compensation via debit card. The debit card process can take up to 8 weeks to be received and an electronic fund transfer takes approximately 10 days to appear in the account. We will also offer the option of being compensated with Veterans Canteen Service coupons (Canteen Bucks).

A subset of Veterans randomized to the direct referral arm will be invited to complete a one-time qualitative interview regarding their experiences in the brief CBT program. We will recruit a total of 28 participants that fall into 3 categories: 1) 4 Veterans with no bCBT engagement (0 sessions), 2) 4 Veterans with little engagement in bCBT (1-3 sessions), and 3) 20 Veterans who fully engaged in treatment (4 or more sessions). The third group will be further stratified to include 10 who opted for and 10 who declined VVC-H. The interview will last 30-45 minutes, and Veterans will be compensated \$30 for their time completing the interview.

A second subset of 24 randomized Veterans will be invited to complete a one-time qualitative interview (see Appendix 7B) regarding barriers to treatment and research access for African American and Hispanic Veterans. These Veterans will be stratified by race/ethnicity (12 African American; 12 Hispanic) based on self-reported racial/ethnic identity, which will be confirmed using the Multigroup Ethnic Identity Measure (MEIM2). Interviews will last approximately 60 minutes, and will be audio recorded and professionally transcribed. Participants will be compensated \$75 if they complete this qualitative interview. Veterans may be compensated up

to a maximum of \$225.00 if they complete all study follow-up assessments and both qualitative interviews.

6.0 Reporting

- Include procedures for reporting unanticipated problems, serious adverse events, and protocol deviations.
- Include information about whether the study has a Data Monitoring Committee and if so, how often it will meet.

All unanticipated serious adverse events (U-SAEs) and unanticipated serious problems (UAPs) will be reported to the VA Central IRB within five business days. U-SAEs will be reported to VA Central IRB regardless of their relationship to the research. All protocol deviations, violations, and/or noncompliance will be reported to the VA Central IRB within five business days of the reporting individual becoming aware of the occurrence.

Safety information, including SAEs/UAPs, that will be collected:

During completion of the study assessment timepoints the participants mental health will be accessed via questions administered. Participants demonstrating increased mental health distress, based upon responses to the assessment, will be evaluated and referred for additional assessment and intervention as needed. Participants in need of immediate treatment (e.g., active psychosis or suicidal intent) will be referred for appropriate services with VA upon identification. Study staff will follow up on any positive responses to items involving suicidal thinking, using a structured crisis-assessment protocol (see Appendix 5). Participants who express suicidal ideation will be forwarded to a study investigator who will triage and refer for care as appropriate.

All occurrences of events resulting in a participants' death, life threatening experience, hospitalization, prolonged hospitalization, or persistent or significant disability will be documented. Any occurrence of an event that results in the need for medical or other interventions to prevent any of the above listed outcomes will be documented as well. As such, any participants identified as having an immediate mental or physical health issue will be referred to care as appropriate.

Frequency/methods of safety-related data collection:

Collection of safety information will commence when the first participant is enrolled in the study. Safety information may be collected either 1) during baseline and follow up assessments, 2) during bCBT sessions, or 3) during telephone contacts with participants made for purposes of

scheduling assessments and/or treatment sessions. All participants will complete comprehensive assessments via telephone at baseline and at 4-, 8-, and 12-month follow-ups. Symptoms of anxiety, depression, and suicidal ideation will be assessed at these time points. Secondly, the Research Coordinator or RA will periodically contact patients to schedule study-related appointments. The participants or other informants may report information related to their safety at those times.

Conditions that would trigger an immediate suspension of the research:

This intervention will compare a brief, structured cognitive-behavioral intervention with usual care practices in VA PCMH. The active treatment, bCBT, utilizes well-established psychotherapeutic techniques to enhance patients' self-management of anxiety. No medications, invasive procedures, or untested techniques will be used. We do not anticipate the occurrence of events that would necessitate the immediate suspension of research because of 1) the low probability of adverse events from the intervention in either arm of the study, 2) all participants will continue to receive usual care services within the VA, and 3) no treatment will be withheld from any participants.

Specify procedures to determine when and how to notify individual participants or their health care providers of findings that may affect the participant's health or welfare:

The decision to contact a patient and/or their health care provider regarding patient welfare can be made in two ways. First, the Project Coordinator, RA, or independent evaluators will conduct routine checks on participants' safety and well-being, including an assessment of suicidal ideation, during baseline and follow up assessments. These study personnel will notify the patient and/or their healthcare provider as necessary.

Second, data and safety monitoring is expected to be conducted at both the local and national levels. At the local level, data and safety monitoring will occur for any identified adverse events. Any participants identified as having an immediate mental or physical health issue will be referred to care as appropriate. Participants will also be assessed for suicidality if a positive response is given to item 9 on the PHQ-9 measure. Responses to the suicide assessment will be reviewed with a licensed psychologist ([name], [name], [name], [name], or [name]) to determine the level of severity and if additional intervention is warranted.

At the national level, the study is under review by the VA's Data and Safety Monitoring Board (DSMB). We will continue to provide the national DSMB with comprehensive annual and semi-annual reports for formal independent review of study safety and recruitment practices.

7.0 Privacy and Confidentiality

- Describe whether the study will use or disclose subjects' Protected Health Information (PHI).
- Describe the steps that will be taken to secure the data (e.g., training, authorization of access, password protection, encryption, physical controls, Certificates of Confidentiality, and separation of identifiers and data)
- If data and biological specimens will be banked, specify

The use of de-identified, identified, and coded data will be utilized for participants in this study. Protected health information (PHI) obtained from patient participants will include: name, age, date of birth, home address, contact phone number, last 4 digits of their social security number (which allows us access to their medical record). PHI requested from enrolled clinicians will be restricted to their name. Information obtained about participants (clinician and veteran) will be kept strictly confidential and not disclosed.

Each participant (clinician and veteran) in the study will receive a unique ID number to increase confidentiality. Data obtained from participants will be maintained in a password protected electronic database. Data and audio recordings will be limited to the study team and stored on VA computers (behind the VA firewall) under Drive:M. As another level of security, access to study folders will be restricted to study team members listed on the delegation of authority. In addition, all electronic data files will be password protected for additional security. To maintain privacy, assessments and interviews will be conducted in one of several private interview rooms available or in the study staffs' office. Private interview rooms will be scheduled for use at the time the assessment is scheduled. All electronic data files will be maintained within the VA setting and behind the VA firewall. Access to research records will be restricted to the Co-PIs and project staff.

Although data from bCBT sessions and interviews from the exploratory aim are being recorded, only data from qualitative interviews conducted for the exploratory aim will be transmitted for transcribing purposes. Approved staff from the VA Salt City (VASLC) will transcribe the Pragmatic Trial of brief CBT for Anxiety in Primary Care audio files. The VASLC has a Professional Transcription Service available to VA sites and monitored by their own IRB. The audio recordings to be transcribed by VASLC staff will be labeled by the subject's unique alphanumeric code and saved behind the VA Firewall in [name] secure shared project folder on the M drive. The VASLC transcription staff will be given access to a sub-folder within [name] secure project folder. Approved study staff will place a copy of the audio files in this folder for an approved VASLC transcriptionist to access for the purposes of transcription. The VASLC transcriptionist will transcribe each interview verbatim and save the completed transcript in the sub-folder using the same alphanumeric code. No data (audio files, in process transcripts, or completed transcripts) will leave the Michael E. DeBakey VAMC secure research server.

As completed transcripts become available, approved study staff will move these files from the transcripts sub-folder into another sub-folder that is only accessible to study staff, where they will be stored and accessed for qualitative analyses.

All project staff are required to have undergone focused training on privacy, the protection of human subjects, research methods and the importance of integrity in the research process. Houston VA HSR&D IQuEST Computing Center also requires all project staff to review the Data Security Compliance Agreement which describes the center's data security protocol. Each project staff member must sign an acknowledgement that they have reviewed the policy and agree to follow the policy before accessing data. The Houston VA HSR&D IQuEST Computing Center data security policy conforms with current VA policies and has been reviewed and approved by the MEDVAMC Chief Information Officer, Information Security Officer, and Privacy Officer.

